^c Results of safety laboratory testing (haematology and clinical chemistry at a minimum) must be available within 72 hours prior to dosing and must be reviewed by the investigator prior to each administration of AZD4573. To initiate Cycle 1 and subsequent cycles, haematology and chemistry criteria in inclusion criteria 10, 13, and 14 shall be met. In addition, during AZD4573 treatment, dose modification and discontinuation guidelines are provided in Section 10.6.1.

^d Mandatory exploratory CCI analysis will be performed any time a bone marrow analysis is performed.

^e The follow-up visit will be performed 30 days (± 7 days) after the last dose of all study drug. Disease assessments will be repeated at this visit if they have not been performed within 9 weeks if the participant discontinued before Week 26, or 12 weeks if the participant discontinued after Week 26.

Abbreviations: ACTH, adrenocorticotrophic hormone; ECG, electrocardiogram; ECHO, echocardiogram; ECOG, Eastern Cooperative Oncology Group; FU, follow-up; IgA, immunoglobulin A; IgG, immunoglobulin G; IgM, immunoglobulin M; IV, intravenous; LTFU, long-term follow-up; MUGA, multigated acquisition; PK, pharmacokinetic; PTCL, peripheral T-cell lymphoma; SoC, standard of care; SOI, start of infusion; TLS, tumour lysis syndrome; TSH, thyroid stimulating hormone; WOCBP, women of childbearing potential.

10.2 Introduction – Module 1

Module 1 of this study will evaluate the efficacy, safety, and tolerability of AZD4573 monotherapy in participants with r/r PTCL or r/r cHL. For an overview of the study design see [Figure 5](#).

10.3 Objectives and Endpoints – Module 1

Type	Objectives	Endpoints
Primary		
Efficacy	To assess the efficacy of AZD4573 by evaluation of objective response rate.	
Endpoint based on Lugano response criteria for malignant lymphoma (Cheson et al 2014):
– ORR, defined as the proportion of participants who have a tumour response (CR and PR)^a
Secondary		
Efficacy	To assess efficacy of AZD4573 by evaluation of tumour response and OS.	
Endpoints based on Lugano response criteria for malignant lymphoma (Cheson et al 2014):
– CR rate– DoR– PFSOS

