10.4.1 Module 1 Design: AZD4573 monotherapy

Module 1 is non-randomised and will consist of 2 r/r PTCL cohorts and 1 r/r cHL cohort; see Figure 5 and Table 10 below for planned participant numbers.

Each cohort will include an intra-participant dose ramp-up, starting at 6 mg AZD4573 (Figure 6). The target dose following the ramp-up is 12 mg attained on Week 3 of Cycle 1. During the first cycle, participants will receive a single dose of AZD4573 once weekly beginning with 6 mg Week 1, 9 mg Week 2, and 12 mg for each of Weeks 3 to 5.

Every cycle beyond Cycle 1 will be 3 weeks in length and participants will receive 12 mg infusions of AZD4573 once weekly until progression.

Figure 6 **Module 1 AZD4573 Monotherapy Dosing Regimen in PTCL and cHL including Intra-Participant Dose Ramp-Up**

Abbreviations: cHL, classical Hodgkin Lymphoma; D, day; PTCL, peripheral T-cell lymphoma; Q1W, once weekly.

A comprehensive initial review of all safety and PK/PD data will be conducted in approximately the first 6 participants of each cohort (safety run-in), with separate SRCs for each cohort executed independently. The safety assessment will be undertaken by the SRC and is detailed in Section 10.4.4. The study procedures and safety assessments undertaken for the first cycle will be as per the SoA (Table 9). Each cohort will have a separate dose confirmation, assessed independently by the SRC, to assess safety and PK/PD data compared to the known profiles in the first time in human study (Study D8230C00001) lymphoma population.

These SRC reviews will confirm whether the RP2D for lymphoma (IV infusion 12 mg once weekly, including intra-participant ramp-up) is safe and tolerable or if additional dose optimisation is indicated at a revised dose and/or schedule. All cohorts can be opened and delivered independently of each other.

The role and responsibilities of SRC members, as well as the purpose and timing of the SRC meetings are described in the SRC Charter.

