10.6.1 Dose Modification

Dose modification and discontinuation guidelines for haematological and non-haematological toxicities (excluding abnormal liver chemistry test results) are shown below in [Table 11](#). Dose modifications for AZD4573 for abnormal liver chemistry test results are described in [Table 12](#).

In general, if a participant experiences a Grade 1 or Grade 2 haematological or non-haematological toxicity, no dose modification is required. If a participant experiences a Grade 3 or Grade 4 toxicity, not attributable to the disease or disease-related processes under investigation, dosing will be interrupted and/or the dose reduced (see [Table 11](#) for recommended dose modifications for AZD4573) and supportive therapy administered as required. If the toxicity resolves or reverts in line with the dose modification guidelines below and the participant was showing clinical benefit, treatment with study treatment(s) may be restarted.

If the toxicity does not resolve in line with the dose modification guidelines below, then the participant should be discontinued from the study treatment and observed until resolution of the toxicity. Maximal drug interruption allowed for AZD4573 is 21 consecutive days; in cases where more than 21 days are needed, a decision to continue, modify, or discontinue study treatment will be made on a case-by-case basis in consultation with the principal investigator and the Study Physician.

Table 11 Recommended Dose Modifications for AZD4573

Event ^a	Occurrence	Action with AZD4573	
Tumour Lysis Syndrome (TLS)			
Changes in uric acid, potassium, phosphorus, creatinine or calcium, or symptoms suggestive of TLS	Any	For any abnormal changes present before dosing, initiate supportive therapy and hold drug for up to 7 days. If not resolved, reduce by 1 dose level.	
		For events of Howard Grade 1 or 2 TLS, resume at same dose level upon resolution.	
		For first occurrence of Howard Grade 3 TLS resume at the same dose upon resolution to Grade 1.	
		For second occurrence of Howard Grade 3 TLS, after resolution to Grade 1, reduce dose by 1 dose level when re-starting AZD4573 except events that in the opinion of the investigator, in consultation with the Study Physician, are not dose limiting.	
		For subsequent occurrences of Howard Grade 3 TLS, further re-challenge and dose level to be discussed with the Study Physician.	
For events of Howard Grade 4 TLS, discontinue AZD4573.			

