Non-haematological toxicities (except liver dysfunction and TLS)			

Event ^a	Occurrence	Action with AZD4573
Grade 3 or 4 non-haematological toxicities	First occurrence	
Withhold dosing with AZD4573 until the toxicity has resolved to Grade 1, but no longer than 21 days^b.
 
Adequate supportive therapy as per Institutional guidelines should be given.
 
After resolution of Grade 3 event to Grade 1, AZD4573 therapy may be resumed at the same dose. No dose modification is required.
 
After resolution of Grade 4 event to Grade 1, reduce dose by one dose level when re-starting AZD4573.

	Second occurrence	
Withhold dosing AZD4573 up to 21 days^b.
 
Adequate supportive therapy as per Institutional guidelines should be given.
 
After resolution to Grade 1, reduce dose by one dose level when re-starting AZD4573.
 
If no resolution within 21 days discontinue AZD4573^b.

	Third occurrence	Discontinue AZD4573.
Haematological Toxicities		
Grade 3 or 4 neutropenia without fever or infection, lasting > 7 days despite growth factor support	First occurrence	
Withhold dosing AZD4573 until Grade \leq 2 or baseline level.
 
Restart at same dose level following resolution.

	Second and subsequent occurrences	
Withhold dosing AZD4573 until Grade \leq 2 or baseline level.
 
Restart with 1 dose level reduction following resolution.
 
In case of subsequent occurrences, dosing may be modified to skip weekly dose(s) (eg, 2 weeks on/1 week off or to 1 week on/1 to 2 weeks off), after discussing with the Study Physician.

Grade 3 or 4 neutropenia with infection or fever	First occurrence	
Withhold dosing AZD4573.
 
To reduce the infection risks associated with neutropenia, G-CSF may be administered with AZD4573 if clinically indicated/required as per Institutional practice.
 
Consider secondary prophylaxis with G-CSF as per ASCO/ESMO guidelines. Once the toxicity has resolved to \leq Grade 2 or to baseline level, AZD4573 therapy may be resumed at the same dose.

	Second occurrence	
Withhold dosing AZD4573.
 
Consider using G-CSF as clinically indicated/as per Institutional practice. Follow dose reduction guidelines when resuming treatment with AZD4573 after resolution.
 
Reduce dose by 1 dose level.

Event ^a	Occurrence	Action with AZD4573
	Third occurrence	Discontinue AZD4573.

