10.6.2 Prevention and Toxicity Management of Risks for AZD4573 Monotherapy

This section provides recommendations for treatment of potential toxicities associated with AZD4573, and guidance about modifying the dose of AZD4573 due to those toxicities. For complete safety information refer to the IB for AZD4573.

Generally, Grade 1 or 2 non-haematological and/or haematological toxicities do not require AZD4573 dose reductions and should be managed as medically indicated (with or without short dose interruptions) by the treating physician. Grade 3 and 4 toxicities require dose modifications, temporary treatment interruptions, or discontinuation of AZD4573. These are described in [Table 11](#) and [Table 12](#) in the Section [10.6.1](#) (Dose Modification – Module 1).

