10.6.2.5 Neutropenia and Febrile Neutropenia

Neutropenia and febrile neutropenia are important identified risks for participants treated with AZD4573. In the presence of CTCAE Grade 3/4 neutropenia, participant's blood counts should be monitored, using local laboratories, at least every 48 hours until recovery.

In the clinical setting to date, Grade 3/Grade 4 neutropenia (~ 45% to 50%) has been observed in several participants with an onset around 24 hours after dosing AZD4573 monotherapy. Usually, neutrophils recovered spontaneously even without G-CSF. However, colony-stimulating factors including G-CSF or pegylated G-CSF has been shown to work rapidly and may be used according to each investigator site's institutional guidelines. Anti-infective prophylaxis including anti-fungal prophylaxis should be used according to institutional guidelines. Anti-viral or cotrimoxazole prophylaxis may not be used unless CD4 helper cell counts are less than 100 to 200 per microlitre.

Primary prophylaxis with G-CSF is not generally recommended. Anti-infective prophylaxis (antibiotics and antifungals) should be given in accordance with local hospital guidelines and International National Comprehensive Cancer Network/European Society for Medical Oncology/American Society of Clinical Oncology guidelines.

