10.6.3 Criteria for Restarting Treatment

The criteria to be met before a participant receives further study drug infusions following a pause in treatment, either within 1 cycle or between cycles, is as below:

All participants:

- 1 Participant has recovered from all treatment-related non-haematological toxicity to CTCAE Grade ≤ 2 .
- 2 Recovery of neutrophils $> 1000/\mu\text{L}$ and platelets $> 75000/\mu\text{L}$ or $> 50000/\mu\text{L}$ with bone marrow involvement.
- 3 Participant has recovered from all hepatic toxicity events within the timeframes described in Table 12 above. If biochemical changes in transaminase(s) and total bilirubin are consistent with the definition of HL, the participant may continue to receive study drug only if all abnormalities have resolved within the timeframes specified in Table 5 above, there are no symptoms of liver injury and INR has not increased above $1.5 \times \text{ULN}$ (or $1.5 \times \text{baseline}$). In these circumstances the participant must be made aware of the unknown potential for liver damage with continued exposure to AZD4573 prior to retreatment. Documentation of continued consent is required.

- 4 Recovery of uric acid to < ULN.
- 5 Recovery of changes in uric acid, potassium, phosphorus, creatinine or calcium, or symptoms suggestive of TLS as defined in [Table 11](#).

10.7 Discontinuation of Study Intervention and Participant Discontinuation/Withdrawal – Module 1

See the SoA (Section [10.1.2](#)) for data to be collected at the time of intervention discontinuation and follow-up and any further evaluations that need to be completed.

Please refer to Section [7](#) (Core protocol) for information on discontinuation of study intervention and participant discontinuation/withdrawal.

10.8 Study Assessments and Procedures – Module 1

- Study procedures and their timing are summarised or linked to in the SoA. Protocol waivers or exemptions are not allowed.
- Immediate safety concerns should be discussed with the sponsor immediately upon occurrence or awareness to determine if the participant should continue or discontinue study intervention.
- Adherence to the study design requirements, including those specified in the SoA, is essential and required for study conduct.

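### For neutropenia without fever or infection, the general text and Table 11 give different Grade 3/4 dosing instructions at within-cycle infusions, and the protocol does not say which governs

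*Protocol*

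**What the plan says.** **General text.** Protocol Section 10.6.1 states that for a Grade 3 or 4 toxicity not caused by the disease "dosing will be interrupted and/or the dose reduced", and refers to Table 11. Section 10.6.2 states: "Grade 3 and 4 toxicities require dose modifications, temporary treatment interruptions, or discontinuation of AZD4573". Neither sentence mentions how long the toxicity must last or whether it was treated.

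**Table 11.** The only row for neutropenia in a participant without fever or infection is "Grade 3 or 4 neutropenia without fever or infection, lasting > 7 days despite growth factor support". The febrile or infected row carries neither condition.

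**Growth factor.** Table 8 (Section 6.5) bars prophylactic G-CSF from Cycle 1 Day 1 and allows it later on medical grounds. Section 10.6.2.5 leaves its use to site guidelines and adds: "Usually, neutrophils recovered spontaneously even without G-CSF".

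**Other neutrophil criteria.** Footnote c to the Schedule of Activities (Section 10.1.2), repeated in Section 10.8.2.5, says: "To initiate Cycle 1 and subsequent cycles, haematology and chemistry criteria in inclusion criteria 10, 13, and 14 shall be met". Criterion 13 sets a neutrophil count of at least 1000 cells/mm³ (Table 5). Section 10.6.3 asks for more than 1000/µL, but only after a pause in treatment.

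**Non-haematological recovery.** For a first Grade 3/4 event Table 11 says "Withhold dosing with AZD4573 until the toxicity has resolved to Grade 1". Section 10.6.3 lists as a restart condition "Participant has recovered from all treatment-related non-haematological toxicity to CTCAE Grade" 2 or lower.

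**The concern.** A site with a participant in afebrile Grade 3/4 neutropenia before a Week 2 or Day 8 infusion finds general text calling for action and a table whose row does not apply. One site may follow the text and hold; another may follow the table and infuse. Both could claim to be compliant.

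The row also makes the action depend on a treatment that the protocol leaves optional. Read literally, a participant who is never given growth factor cannot meet it at any duration.

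Neutropenia is an important identified risk (Table 2) and an adverse event of special interest (Section 8.3.6), so participant safety comes first. There is also a statistical interest. The SAP (Section 5.6.1) summarises dose delays and relative dose intensity, and the Safety Review Committee reviews about the first 6 participants in each cohort. Those data could partly reflect which passage a site followed.

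**Working it through.** The plan gives no figure to reproduce here. The check is a timing calculation, a count of infusions and a comparison of passages.

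**Inputs**
- Dosing interval: 7 days (Section 10.4.1: "participants will receive 12 mg infusions of AZD4573 once weekly until progression"; Cycle 1 is also weekly).
- Dosing window: ±2 days (Section 10.1.2, Table 9; SAP Section 5.6.1.1).
- Onset: about 24 hours after infusion (Section 10.6.2.5), taken as day 1, with day 0 as a check.
- Row condition: more than 7 days, with growth factor given (Table 11).
- Rate of Grade 3/4 neutropenia: about 45% to 50% (Section 10.6.2.5).
- Planned response-evaluable participants: 21 per cohort (Section 10.9.2).

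**1. Duration at the next infusion.** Days elapsed = interval − onset day.

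| Interval | Onset day 1 | Onset day 0 | More than 7 days? |
|---|---|---|---|
| 7 (nominal) | 7 − 1 = 6 | 7 − 0 = 7 | No |
| 5 (next dose 2 days early) | 5 − 1 = 4 | 5 − 0 = 5 | No |
| 9 (next dose 2 days late) | 9 − 1 = 8 | 9 − 0 = 9 | Yes |
| 11 (prior dose 2 days early, next 2 days late) | 11 − 1 = 10 | 11 − 0 = 11 | Yes |

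On the nominal schedule a new episode does not meet the duration condition at the next infusion. It first can at the second infusion after the causative dose (14 − 1 = 13 days). An episode that began before the previous dose has lasted more than 7 days by the next one and meets it too.

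**2. Infusions outside the cycle-start criterion.** Footnote c applies on Day 1 of each cycle. In Cycle 1 that leaves Weeks 2 to 5, which is 5 − 1 = 4 of 5 infusions. In each later cycle it leaves Days 8 and 15, which is 3 − 1 = 2 of 3. Section 10.6.3 applies only once a dose has been paused, so it does not decide whether to pause. For these infusions footnote c and Section 10.8.2.5 point to Section 10.6.1, which contains both the general sentence and the table.

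**3. Same count, different day.** A count below 1000 blocks Day 1 of a cycle, whatever its duration or treatment. The same count on Day 8 meets no stated numerical threshold. Equating Grade 3 with a count below 1000 would be an assumption, since the CTCAE cut-offs are not printed in the documents.

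**4. Same course, different treatment.** Take two participants with identical counts, both afebrile and at Grade 3 for 9 days. If one received G-CSF and the other did not, only the first meets the row. Under the general sentence both would have dosing interrupted and/or reduced.

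**5. Number affected.** 0.45 × 21 = 9.45 and 0.50 × 21 = 10.5, so about 9 to 11 per cohort would have Grade 3/4 neutropenia of any kind. Those affected are the subset who are afebrile and still at Grade 3/4 when a within-cycle dose is due. Neither share is given, so the range is 0 to about 11 of 21.

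**6. Secondary points.** Table 11 holds Grade 3 thrombocytopenia without bleeding at any occurrence, but its bleeding row requires a transfusion. Grade 3 with bleeding and no need for transfusion has no row. For non-haematological toxicity, Table 11 gives recovery to Grade 1 and Section 10.6.3 gives Grade 2 or lower, without saying which governs.

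**The case against.** The strongest reply is that there is no contradiction. Section 10.6.1 opens its general rule with a hedge and refers to a table headed as recommendations, so the table can be read as refining the text. Alternatively, the general sentence still binds where no row fits, and then short or untreated episodes are already covered. Each reading is coherent, but they lead to different actions and the protocol does not choose between them. The hedge also sits in the sentence on Grade 1 and 2; the Grade 3/4 sentences in both sections are directive.

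A second reply is that other safeguards exist. Counts must be reviewed by the investigator before every dose (footnote c). Grade 3/4 neutropenia requires counts at least every 48 hours until recovery (Section 10.6.2.5). Section 6.6 lets the investigator halt or reduce dosing. This stands as mitigation: a reader might infer unguarded dosing, and the documents do not support that. But none of these safeguards sets a threshold, and discretion permits variation between sites.

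Third, a reader might infer that the Table 11 row can never be met at the next weekly infusion. That is not so: the +2-day window gives 8 days, and an episode older than the previous dose also qualifies.

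Fourth, the two non-haematological recovery grades can both be satisfied if Section 10.6.3 is read as a minimum and Table 11 as a stricter condition for the event that caused the hold. That is fair. The defect there is unstated precedence, not a proven conflict.

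**Conclusion.** The point holds as a conflict of instructions with no stated precedence, confined to within-cycle infusions: Weeks 2 to 5 of Cycle 1, and Days 8 and 15 of later cycles. Under the table, the action depends on discretionary growth factor, and on the nominal schedule a new episode reaches the next infusion after about 6 days, before the row can apply. It should be corrected because it bears on participant safety and on consistent dosing across sites.

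The timing result assumes onset at about 24 hours and an exact 7-day interval. The ceiling of about 9 to 11 of 21 assumes that the quoted rate carries over to these diseases; Section 2.2 says the first-in-human study enrolled no PTCL or cHL patients. A reader might take that figure as the number affected, but it includes febrile cases and episodes that resolve before the next dose.

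A reader might also infer that the committee's dose confirmation or the response rate is compromised. The documents do not show this. The committee reviews all relevant data, its 25% trigger counts discontinuations for related events rather than holds, and no effect on the primary endpoint can be derived. The thrombocytopenia gap and the differing recovery grades are secondary.

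**What to change.** Reconcile the general sentences in Sections 10.6.1 and 10.6.2, the neutropenia and thrombocytopenia rows of Table 11, the cycle-start criterion in footnote c and Section 10.8.2.5, and the restart list in Section 10.6.3. State which passage governs at each weekly pre-dose blood count, including when no Table 11 row applies or when growth factor was not given. State also which recovery grade governs for non-haematological toxicity. The clinical team decides the rule; none is proposed here.

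The cost is amendment wording. Haematology before every infusion is already required, so no new assessment is needed. Depending on the rule chosen, some doses may be given or delayed differently from how some sites now read the protocol.

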Grade 3 thrombocytopenia without bleeding	Any	Withhold AZD4573 until Grade \leq 2 or baseline level. Restart AZD4573 at the same dose level.
Grade 4 thrombocytopenia without bleeding requiring blood or platelet transfusion	First occurrence	Withhold AZD4573 until Grade \leq 2 or baseline level. Restart AZD4573 at the same dose level.
	Second occurrence	Withhold AZD4573 until Grade \leq 2 or baseline level. Restart AZD4573 with 1 level dose reduction. If not recovered to Grade \leq 2 or baseline level discontinue.
	Third occurrence	Discontinue AZD4573.
Grade 3 or 4 thrombocytopenia with bleeding requiring blood or platelet transfusion	First occurrence	Withhold AZD4573 until Grade \leq 2 or baseline level. Restart AZD4573 with 1 level dose reduction. If not recovered to Grade \leq 2 or baseline level discontinue.
	Second occurrence	Discontinue AZD4573.

^a Adverse reactions are graded using NCI CTCAE version 5.0.

^b In cases where more than 21 days are needed, a decision to continue, modify, or discontinue study treatment will be made on a case-by-case basis in consultation with the principal investigator and the Study Physician.

Abbreviations: ANC, absolute neutrophil count; ASCO, American Society of Clinical Oncology; ESMO, European Society for Medical Oncology; G-CSF, granulocyte-colony stimulating factor.

Dose modifications for AZD4573 for abnormal liver chemistry test results are described in [Table 12](#).

Table 12 Recommended Dose Modifications for AZD4573 for Abnormal Liver Chemistry Test Results

Event ^a	Action
Isolated^b elevations in ALT, AST, or bilirubin	
Grade 1 Isolated ALT/AST \leq 3 \times ULN or Isolated Bilirubin \leq 1.5 \times ULN	Maintain current dose level. Monitor ALT, AST, ALP, and bilirubin at least 1x per week.

Event ^a	Action
Grade 2 Isolated ALT/AST > 3 to $\leq 5 \times$ ULN or Isolated Bilirubin > 1.5 to $\leq 3 \times$ ULN	After 7 days if hepatic enzymes resolve to Grade ≤ 1 , re-challenge at same dose level.
Grade 3 Isolated ALT/AST > 5 to $20 \times$ ULN	If recovered to Grade ≤ 1 within 7 days, allow re-challenge at same dose level. If not recovered to baseline level within 7 days, discontinue AZD4573.
Grade 3 Isolated Bilirubin > 3 to $10 \times$ ULN	If recovered to baseline level within 96 hours (-2/+12 hours) of start of dose allow re-challenge at same dose level. If not, discontinue AZD4573.
Grade 4 Isolated ALT > $20 \times$ ULN or Isolated Bilirubin > $10 \times$ ULN	Discontinue AZD4573.

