Grade 4 Isolated elevation ($\geq 20 \times$ ULN) in AST without concomitant elevation in ALT $\geq 20 \times$ ULN or concomitant elevation in TBL $\geq 2 \times$ ULN that fails to return to baseline level within 7 days from start of dosing	Discontinue AZD4573.
Grade 4^c Isolated AST elevation $\geq 20 \times$ ULN without concomitant elevation in ALT $\geq 20 \times$ ULN or TBL $\geq 2 \times$ ULN	First occurrence If recovered to Grade ≤ 1 or baseline level within 7 days of start of dose allow re-challenge at same dose level.
	Second occurrence If recovered to Grade ≤ 1 or baseline level within 7 days of start of dose allow re-challenge with 1 dose level reduction.
	Third occurrence Discontinue AZD4573.
Concurrent elevations in ALT, AST, or bilirubin (Please also refer to the HL appendix in the CSP for actions to be taken in the event of PHL)	
ALT or AST $\geq 3 \times$ ULN with TBL $\geq 2 \times$ ULN (PHL) AND INR $\geq 1.5 \times$ ULN (or $\geq 1.5 \times$ baseline if elevated at baseline) of any duration	Discontinue AZD4573.

Event ^a	Action
ALT or AST $\geq 3 \times$ ULN with the appearance of fatigue, nausea, vomiting, right upper quadrant pain or tenderness, fever, rash, and/or eosinophilia $> 5\%$	Discontinue AZD4573.
ALT or AST $\geq 3 \times$ ULN and TBL $\geq 2 \times$ ULN where TBL does not return to baseline level within 96 hours (-2/+12 hours) from start of dose and/or AST or ALT do not return to baseline level within 7 days from start of dose	Discontinue AZD4573.
Grade 3 elevation ($\geq 5 \times$ ULN) in ALT or AST with TBL elevation above baseline level or ULN, but $< 2 \times$ ULN that do not return to baseline level within 7 days	Discontinue AZD4573.
ALT and AST $\geq 3 \times$ ULN with concomitant TBL $\geq 2 \times$ ULN, NO increase in INR $\geq 1.5 \times$ ULN (or 1.5 \times baseline), and NO fatigue, nausea, vomiting, right upper quadrant pain or tenderness, fever, rash, and/or eosinophilia $> 5\%$	If recovered to Grade ≤ 1 or baseline level within 96 (-2/+12) hours, re-challenge at same dose level ^c .

^a Adverse reactions are graded using NCI CTCAE version 5.0.

^b Elevations in ALT or AST are considered isolated if bilirubin remains below Grade 1, and elevations in bilirubin are considered isolated if ALT and AST remain below Grade 1.

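### Protocol Table 12 uses two recovery thresholds at one deadline, so in three places a liver value at Grade ≤1 but above baseline triggers both re-challenge and discontinuation

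*Protocol*

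**What the plan says.** Table 12 in Protocol 10.6.1 gives the action on AZD4573 for abnormal liver tests. Three events carry both a re-challenge rule and a discontinuation rule.

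1. **Isolated Grade 3 ALT/AST** (above 5 and up to 20 × ULN). A single cell names recovery to Grade ≤1 and goes on: "within 7 days, allow re-challenge at same dose level. If not recovered to baseline level within 7 days, discontinue AZD4573".
2. **Isolated Grade 4 AST** (≥20 × ULN, without ALT ≥20 × ULN or total bilirubin (TBL) ≥2 × ULN). One row discontinues for an elevation "that fails to return to baseline level within 7 days from start of dosing". The next row starts from Grade ≤1 "or baseline level within 7 days of start of dose allow re-challenge at same dose level" at the first occurrence, and "or baseline level within 7 days of start of dose allow re-challenge with 1 dose level reduction" at the second. A third occurrence means discontinuation in any case.
3. **Concurrent elevation.** For ALT or AST ≥3 × ULN with TBL ≥2 × ULN, one row discontinues on a bilirubin limb, "where TBL does not return to baseline level within 96 hours (-2/+12 hours) from start of dose", and on a transaminase limb, "and/or AST or ALT do not return to baseline level within 7 days from start of dose". The last row covers a narrower case: both ALT and AST ≥3 × ULN, TBL ≥2 × ULN, no INR rise, "and NO fatigue, nausea, vomiting, right upper quadrant pain or tenderness, fever, rash, and/or eosinophilia" above 5%. Its action starts from Grade ≤1 "or baseline level within 96 (-2/+12) hours, re-challenge at same dose level".

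Table 12 puts the Grade 1 ceiling at 3 × ULN for ALT/AST and 1.5 × ULN for bilirubin. It does not define baseline level.

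**The concern.** A dose-modification rule should send each result to one action. Here the re-challenge limb accepts Grade ≤1 and the discontinuation limb demands baseline, so a result between the two meets both. Two sites holding the same result could take opposite actions and each point to the table.

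The consequences are hard to undo. Protocol 7.1 bars restarting a participant whose treatment was stopped for safety. In the other direction, a participant may be re-exposed whom the sponsor meant to take off drug. Protocol Table 2 lists transaminase increase, and bilirubin increase with it, as important identified risks. AEs leading to discontinuation are also a safety endpoint (Protocol 10.3), and related ones in more than 25% of participants prompt Safety Review Committee evaluation (Protocol 7.1.1 and 10.4.4). Uneven application therefore reaches study-level monitoring too.

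**Working it through.** There is no plan figure to reproduce. The check reads each row as a condition and an action and applies it to the same state.

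**Rule.** Re-challenge applies if the value at the deadline is at or below the Grade 1 ceiling. Discontinuation applies if the value is above baseline. Both apply when baseline < value ≤ Grade 1 ceiling.

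**Illustration.** The participant values are assumed, in × ULN. Baseline is the participant's own value, INR is normal and no listed symptom is present.

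| Case | Baseline | Peak | At deadline | Re-challenge | Discontinue |
|---|---|---|---|---|---|
| Place 1, ALT | 0.8 | 8 | 2.0, day 7 | yes (2.0 ≤ 3) | yes (2.0 > 0.8) |
| Control | 0.8 | 8 | 0.8, day 7 | yes | no |
| Control | 0.8 | 8 | 3.5, day 7 | no (3.5 > 3) | yes |
| Control | 2.5 | 8 | 2.0, day 7 | yes | no (2.0 < 2.5) |
| Place 2, AST | 0.8 | 25 | 2.0, day 7 | yes (2.0 ≤ 3) | yes (2.0 > 0.8) |
| Place 3, TBL | 0.6 | 2.5 | 1.3, 96 h | yes (1.3 ≤ 1.5) | yes (1.3 > 0.6) |

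In the place 3 row, ALT and AST both peak at 4 and are 2.0 at 96 hours, which is also Grade ≤1. The place 2 result is the same at the first and second occurrence.

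**Place 3, ALT/AST limb.** Here the deadlines differ. Take ALT and AST at 2.0 and TBL at its baseline of 0.6 at 96 hours, then ALT at 1.2 on day 7 against a baseline of 0.8. Re-challenge is met at 96 hours and discontinuation only at day 7. Dosing is weekly, so the two rows may be meant as sequential checks. The table does not say so.

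**Meaning of baseline level.** There are three readings for ALT/AST:
- (a) the participant's value: overlap above baseline and up to 3 × ULN;
- (b) the baseline grade, with baseline within ULN (taken as Grade 0, an assumption): overlap above 1 and up to 3 × ULN;
- (c) the baseline grade, with baseline already Grade 1: no overlap.

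For TBL the same readings apply with 1.5 × ULN as the upper limit.

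**Text that might decide between the limbs.**
- Protocol 10.8.2.5 sets the end of repeat testing at baseline in the clinical chemistry bullet, and at baseline or Grade 1 in the liver chemistry bullet. Both concern testing, not dosing.
- Protocol 10.6.2.2 requires permanent discontinuation if values fail to resolve in time, without defining resolution.
- Protocol 10.6.3 item 3 points back to Table 12. For Hy's Law-type changes it requires every abnormality to have resolved, again undefined. It takes those timeframes from Table 5, which holds haematology entry criteria and no timeframes.
- The cycle-start rule (Table 9 footnote c and 10.8.2.5) adds minimum laboratory criteria alongside 10.6.1.

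None of these ranks one limb above the other.

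**The case against.** The strongest reply is that the two limbs differ in force. In places 1 and 2 re-challenge is only allowed, while the other limb is an instruction. The introduction to Protocol 10.6.1 follows the same pattern: treatment may restart if toxicity resolves, and should stop if it does not. An investigator who discontinues breaches neither limb. This favours the stricter reading. It also leaves the Grade ≤1 wording with no effect, because entry criteria already cap baseline ALT/AST at 3 × ULN (Protocol Table 6), and the re-challenge wording in place 3 is not permissive. For place 3, the 10.6.3 requirement that all abnormalities have resolved does weigh against re-challenge at the illustrated values.

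The second reply is oversight. Table 12 is headed as recommendations. Protocol 6.6 requires discussion with the Study Physician before dosing resumes, and Table 12 footnote c requires a documented risk discussion after Grade 4 transaminase increases or potential Hy's Law. Place 3 events are reported as SAEs within 1 day with Study Physician guidance (Appendix E 4.2), and are logged centrally (Protocol 8.3.7). This stands as real mitigation, chiefly for place 3, but it supplies no written threshold.

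A reader might also infer that the rest of the protocol leans towards Grade ≤1. It does not. One 10.8.2.5 bullet uses baseline alone, as do the Table 12 rows for isolated Grade 3 bilirubin and for Grade 3 ALT/AST with TBL below 2 × ULN. The cycle-start rule is only an added minimum.

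**Conclusion.** The contradiction is established in three places: isolated Grade 3 ALT/AST at 7 days, isolated Grade 4 AST (first and second occurrence) at 7 days, and TBL at 96 hours in the narrow concurrent case. It rests on readings (a) or (b) of baseline level and disappears under (c). The ALT/AST limb of place 3 is an unstated sequence, not a proven clash. It should be fixed, since it is a safety rule with two answers, partly mitigated and cheap to correct.

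Three stronger readings are not supported.
- A reader might infer that the 96-hour limit in Protocol 10.6.2.2 also contradicts the 7-day row for isolated Grade 2 bilirubin. That section is about transaminase increases and sends the reader to Table 12, which may control.
- A reader might infer that many participants are affected. The documents give no incidence. Nausea and vomiting occurred in about half of dosed participants (Protocol 10.6.2.4), so the symptom condition may remove many cases from place 3.
- A reader might infer bias in the primary endpoint. SAP 5.2.1.1 uses data up to progression regardless of withdrawal from therapy, and no SAP rule depends on Table 12.

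**What to change.** In each of the three places, use one recovery level for both outcomes. For example: at Grade ≤1 or baseline by the deadline, re-challenge at the stated dose; otherwise discontinue. If the sponsor wants the stricter rule, use baseline alone in both limbs. The protocol already has this single-threshold form in the isolated Grade 3 bilirubin row and in the thrombocytopenia rows of Table 11 that discontinue for non-recovery.

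In the same amendment:
- state whether baseline level means the value or the grade;
- state whether the 7-day ALT/AST check in the concurrent case must also be met before re-challenge;
- use one definition of resolution in Protocol 10.6.2.2, 10.6.3 and 10.8.2.5;
- correct the Table 5 citation in 10.6.3 item 3, where Table 12 appears to be meant.

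The choice of threshold is clinical and belongs to the sponsor. The cost is protocol wording, with no effect on sample size or analysis.
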